## 8 Product Description

### 8.1 General

The Abre system is intended for use in the iliofemoral veins for the treatment of symptomatic venous outflow obstruction.

The Abre system consists of a stent and stent delivery system designed specifically for implantation in the peripheral venous system. The Abre system consists of a flexible self-expanding stent made of a nickel-titanium alloy (nitinol) provided in multiple lengths and diameters and an over-the-wire stent delivery system.

**Table 1** lists the stent diameters and lengths for the Abre stent.

**Table 1: Stent Diameters and Lengths**

		Stent Length (mm)						Nitinol Tube Wall Thickness
		40	60	80	100	120	150	
Stent Diameter (mm)	10	x	x	x	x	x	x	0.018"
	12		x	x	x	x	x	
	14		x	x	x	x	x	
	16		x	x	x	x	x	0.028"
	18		x	x	x	x	x	
	20		x	x	x	x	x	

[figure not shown]
#### 8.1.1 Stent

The Abre stent is a flexible self-expanding nitinol (nickel-titanium alloy) stent provided in multiple lengths and diameters. The stent is laser machined from a continuous seamless piece of nitinol tubing into an open lattice design.

[figure not shown]
A drawing of the laser cut Abre stent is seen in **Figure 1**. There are no welds, joints, or bonds used in the construction of the stent. The Abre stent cell geometry includes three wave peaks between connection bridges. An alternating off-line pattern used for the connection bridges is intended to increase stent flexibility. The Abre stent is designed for durability. Compound radii were applied to specific nodes in order for high strain locations to be further reduced resulting in a higher fatigue life. These radii can be seen in the figures below. After being laser cut, the stent is electropolished and passivated. The Abre stent uses integral nitinol markers for visibility. **Figure 2** is a picture of the finished stent. Upon deployment, the stent achieves its predetermined diameter and exerts an outward force to maintain patency and placement (i.e. no migration) in the target vessel.

Cell lengths and strut widths vary linearly with stent diameter across two groups of stent diameters:

- (1) the 10-14 mm diameter stents, which are cut from a starting tube thickness of 0.018"; and
- (2) the 16-20 mm diameter stents, which are cut from a starting tube thickness of 0.028".

**Figure 1: Abre laser cut pattern**

[figure not shown]
**Figure 2: Abre finished stent**

### 8.1.2 Abre Stent Delivery System

The Abre stent delivery system is an over-the-wire (OTW), 9 Fr, 0.035" guide wire compatible, delivery system for deploying the Abre self-expanding nitinol stent in the iliofemoral vein. The catheter is a triaxial shaft configuration consisting of an inner shaft, a retractable sheath, and an isolation sheath. The inner shaft is PEEK (polyether ether ketone) with a radiopaque Pebax tip. The retractable sheath is a braid reinforced nylon with a PTFE liner. The isolation sheath is High-Density Polyethylene (HDPE). The retractable sheath has one 90% Platinum/10% Iridium radiopaque marker that aids in positioning the catheter. The isolation sheath is attached to the deployment handle assembly via the strain relief. A single luer port is located on the proximal end of the deployment handle. Saline is injected into this port to flush air from the system. The handle assembly contains a thumbwheel actuated deployment mechanism that, along with the isolation sheath, provides control and accuracy during stent deployment. A locking pin prevents the stent from being deployed prior to intended use and must be removed to actuate the thumbwheel.

As the thumbwheel is rotated, a stainless steel Pull Cable is wound onto the thumbwheel and pulls the retractable sheath toward the handle, deploying the stent.

**Figure 3** provides a drawing of the Abre stent delivery system.

**Figure 3: Abre stent delivery system**

Abre system model numbers are listed in **Table 2** for the US and **Table 3** for outside the US. No model numbers were added to the study during the enrollment period.

**Table 2: Abre system model numbers in US**

Model	Stent Ø (mm)	Stent Length (mm)	Working Length (cm)
AB9T10040090	10	40	90
AB9T10060090	10	60	90
AB9T10080090	10	80	90
AB9T10100090	10	100	90
AB9T10120090	10	120	90
AB9T10150090	10	150	90
AB9T12060090	12	60	90
AB9T12080090	12	80	90
AB9T12100090	12	100	90
AB9T12120090	12	120	90
AB9T12150090	12	150	90
AB9T14060090	14	60	90
AB9T14080090	14	80	90
AB9T14100090	14	100	90
AB9T14120090	14	120	90
AB9T14150090	14	150	90
AB9T16060090	16	60	90
AB9T16080090	16	80	90
AB9T16100090	16	100	90
AB9T16120090	16	120	90
AB9T16150090	16	150	90
AB9T18060090	18	60	90
AB9T18080090	18	80	90
AB9T18100090	18	100	90
AB9T18120090	18	120	90
AB9T18150090	18	150	90
AB9T20060090	20	60	90
AB9T20080090	20	80	90
AB9T20100090	20	100	90
AB9T20120090	20	120	90
AB9T20150090	20	150	90

**Table 3: Abre system model numbers outside the US**

Model	Stent Ø (mm)	Stent Length (mm)	Working Length (cm)
AB9G10040090	10	40	90
AB9G10060090	10	60	90
AB9G10080090	10	80	90
AB9G10100090	10	100	90
AB9G10120090	10	120	90
AB9G10150090	10	150	90
AB9G12060090	12	60	90
AB9G12080090	12	80	90
AB9G12100090	12	100	90
AB9G12120090	12	120	90
AB9G12150090	12	150	90
AB9G14060090	14	60	90
AB9G14080090	14	80	90
AB9G14100090	14	100	90
AB9G14120090	14	120	90
AB9G14150090	14	150	90
AB9G16060090	16	60	90
AB9G16080090	16	80	90
AB9G16100090	16	100	90
AB9G16120090	16	120	90
AB9G16150090	16	150	90
AB9G18060090	18	60	90
AB9G18080090	18	80	90
AB9G18100090	18	100	90
AB9G18120090	18	120	90
AB9G18150090	18	150	90
AB9G20060090	20	60	90
AB9G20080090	20	80	90
AB9G20100090	20	100	90
AB9G20120090	20	120	90
AB9G20150090	20	150	90

The Abre system was investigational in the US during the pivotal study enrollment phase and was labeled as such. The label was provided separate from the CIP. The Abre system was approved by FDA on 21/OCT/2020. Outside the US, the Abre system is CE marked and was labeled as such. Labeling was provided in local language for CE marked devices. The CE marked devices were used within intended use as described in the approved IFU for which CE mark has been obtained. In countries where no market release is obtained, the use of the Abre system was limited to the clinical investigation and according the Clinical Investigation Plan. Instructions for Use were available separate from this CIP. The device classification of the Abre system is listed in **Table 4**.

**Table 4: Device Classification**

Device	Classification by Geography	
	USA (FDA)	European Union (MDD)
Abre system	Class III	Class IIb

## 8.2 Manufacturer

The Abre self-expanding venous stent system was manufactured in accordance with standard procedures and specifications under 21 CFR 820 and ISO13485. The manufacturer is listed below:

Medtronic Inc.  
[name]  
Minneapolis, Minnesota 55432  
USA

## 8.3 Packaging

The Abre system was delivered in a sterile package for single use only. The label was provided separate from the CIP.

## 8.4 Intended Population

The Abre system is intended for use in the iliofemoral veins for the treatment of symptomatic venous outflow obstruction.

The Abre stent must not be used in patients in whom anticoagulant or antiplatelet therapy is contraindicated and with known hypersensitivity to nickel titanium (nitinol).

## 8.5 Equipment

Any test equipment critical to be used for assessing endpoints (e.g., Duplex Ultrasound, X-ray, IVUS, venography) will be maintained/calibrated according to the site's standard protocol. Maintenance and calibration reports will be monitored periodically.

## 8.6 Product Training Requirements

The implanting investigator was evaluated to ensure that he/she was qualified by training, education, and experience to implant iliofemoral venous stents. Each implanting investigator was required to meet the predefined minimum requirement of having performed at least 10 iliofemoral venous stent cases in the year prior to site activation. It was also required that the study site had performed at least 20 venous stenting cases in the year preceding site activation.

The implanting investigator was trained on the Abre system including, but not limited to at least the following:

- Instructions for Use of the Abre system
- Bench top model of the Abre system including deployment of at least one stent

No roll-in patients were planned for the pivotal study phase.

Additional training requirements are included in the ABRE Study Training Plan.

## 8.7 Product Receipt and Tracking

All sites were trained on device accountability, including the return of open or unopened devices (for defect, damage, malfunction, expired inventory).

The PI was responsible for maintaining adequate records of the receipt and disposition of all Abre systems as per the Device Accountability Instructions provided in the Investigator Site File.

All sites were required to maintain (investigational) device records that contained the following information on all components shipped to the site for the study:

- (Investigational) device name
- Device model number
- Device lot number
- Date of receipt of device
- Name of person receiving the device
- Name of person using/opening the device (if applicable)
- Date of implant or use (if applicable)
- Subject Identification Number (SID) of subject receiving or using the device (if applicable)
- Disposition (implanted, disposed of, or returned to Medtronic)

For devices that were returned to Medtronic or disposed of, sites were required to document the following additional information:

- The reason for the device being returned to Medtronic or disposed of
- Name of the person who returned or disposed of each device
- Date shipped to Medtronic, if returned
- If device is disposed of, the method of disposal

## 8.8 Product Storage

Where investigational, the sites were required to store devices as labeled and within a secured area away from sunlight that was accessible and controlled only by the assigned, trained study personnel at the site.

Where market-released, the sites were required to store devices as labeled.

## 8.9 Product Return

In the event of a device malfunction of the Abre system prior to, during, or after implant (due to conversion to surgery during the index procedure, stent infection, integrity issues triggering explant or identification during autopsy), the device was to be returned to Medtronic. Sites were instructed to contact their Medtronic clinical study representative to obtain further instruction on device return procedures. All explanted devices were to be analyzed by Medtronic. At the end of the study enrollment period, all remaining investigational devices (in US) were returned to Medtronic.

## 9 Selection of Subjects

### 9.1 Study Population

Patients between 18 and 80 years (inclusive) requiring treatment of a non-malignant venous obstruction within the common iliac, external iliac, and/or common femoral vein were considered for the study if they met all of the inclusion and exclusion criteria (I/E criteria).

### 9.2 Subject Enrollment (Point of Enrollment and Inclusion)

The point of enrollment was the time at which the subject signed and dated the informed consent form.

The point of inclusion was the time at which the subject who signed and dated the informed consent form, adhered to all I/E criteria and the Abre system entered the vasculature.

### 9.3 Subject Screening

Patients identified with symptomatic venous outflow obstruction in the iliofemoral veins requiring a venous stent were screened by the site's investigative team for possible inclusion in the study.

During the course of the study, Medtronic had the option to limit enrollments to specific indications (i.e. acute DVT, postthrombotic syndrome (PTS), or nonthrombotic iliac vein lesion (NIVL)), if needed in order to achieve a distribution that was similar to the literature review used to develop the study performance goals. Investigators were notified of specific indications that would no longer be considered for enrollment. This determination would be made during the screening process, at which time the subject would become a screening failure.

#### **Enrolled**

Patients who met all general screening criteria were asked to participate in the study. If the patient agreed to participate, prior to any study-specific tests or procedures, a personally signed and dated informed consent was obtained. Signing and dating the informed consent form was considered the point of enrollment. Once informed consent was obtained study-specific tests were performed to assess any remaining I/E criteria.

#### **Enrolled – not included**

Consented subjects who did not meet all I/E criteria were to not be treated with the Abre stent. This might have been based on the outcome of imaging during the implant procedure. If subjects left the study before the implant date, safety assessments could be stopped at the date of screening failure. If subjects were

excluded based on failing the I/E criteria during the implant procedure, they were to be followed for 30 days for safety assessment only. No imaging needed to be sent to the core laboratory for these subjects.

### **Included**

Consented subjects who met all study-specific I/E criteria were eligible to be treated with the Abre stent. During the study procedure, the point at which the Abre system entered the vasculature was considered the point of inclusion into the study. Subjects who were implanted with the Abre stent were to be followed for the duration of the study.

Two hundred (200) subjects were included in the ABRE study.

### **Included – not implanted**

This is a sub-category of the Included group. Consented subjects who met all study-specific I/E criteria were treated with the Abre stent. During the study procedure, the point at which the Abre system entered the vasculature was considered the point of inclusion into the study. Those subjects who were not implanted with the Abre stent were to be followed for 30 days for safety assessment only. These subjects were to be included in the primary analysis. The pre-procedure/pre-stenting imaging was to be submitted to the core laboratory. No subjects were included-not implanted in the ABRE study.

The subject's medical record must have indicated that the subject was enrolled in the ABRE Study. Sites were required to maintain a Subject Identification and Enrollment Log.

These subject categories are described in **Table 5**.

[figure not shown]
**Table 5: Description of subject categories**

Subject category	Description
Enrolled	Subjects who signed and dated the informed consent form.  These subjects were to be recorded on the Subject Identification & Enrollment Log.
Enrolled - not included	Subjects who signed and dated the informed consent form and where the Abre system did not enter the vasculature . For example due to not fulfilling all I/E criteria which could only be assessed after the point of enrollment.  These subjects were to be recorded on the Subject Identification & Enrollment Log.
Included	Subjects, who signed and dated the informed consent form, adhered to all I/E criteria and where the Abre system entered the vasculature.  These subjects were to be recorded on the Subject Identification & Enrollment Log.
Included - not implanted	Subjects, who signed and dated the informed consent form, adhered to all I/E criteria and where the Abre system entered the vasculature and the Abre stent was not implanted .

	These subjects were to be recorded on the Subject Identification & Enrollment Log.
--	--

Failure to obtain a handwritten signed and hand-dated informed consent prior to any study-specific procedures constituted a deviation, which is reportable to the Institutional Review Board (IRB)/Ethics Committee (EC) (henceforth referred to as "Ethics Board"), the FDA, and other regulatory authorities as applicable. However, if any required baseline exams (e.g. IVUS, venography, Duplex Ultrasound, blood labs) had been performed as standard of care prior to consenting the patient, they could be used as the baseline/qualifying exams (and will not be considered a deviation), provided they met the following criteria:

- the investigator determined that the exams contained the protocol-required data and were adequate for evaluation;
- the exams were completed within 30 days prior to the scheduled implant procedure.

**Figure 4: Flow-Diagram from Subject Screening to Follow-up**

## 9.4 Inclusion Criteria

Candidates for the ABRE study were appropriate subjects for iliofemoral venous stenting and were required to fulfill all of the following inclusion criteria to be eligible for recruitment in the study:

### General Inclusion Criteria

1. Patient is  $\geq 18$  and  $\leq 80$  years of age;
2. Patient has at least one of the following clinical manifestations (i.e. symptoms and/or signs) of venous disease in lower extremity:
  - a. CEAP score  $\geq 3$ 
  - b. Venous Clinical Severity Score pain score (VCSS)  $\geq 2$ 
  - c. Suspected deep vein thrombosis (DVT);
3. Patient is willing and capable of complying with specified follow-up evaluations at the specified times;
4. Patient has been informed of the nature of the study, agrees to its provisions and has provided written informed consent, approved by the appropriate Ethics Board.

### Imaging-based Inclusion Criteria

5. Patient has diagnosis of non-malignant venous obstruction within the common iliac, external iliac, and/or common femoral vein. The proximal point of the obstruction may extend to the iliac venous confluence of the inferior vena cava and the distal point may be at or above the deep femoral vein. Diagnosis must be made based on objective imaging by using venography and/or intravascular ultrasound (IVUS). Patient must have good inflow involving either the femoral or deep femoral vein being patent and at least a caudal section of the common femoral vein that is free of significant disease;
6. Patient has an obstructive lesion defined as:
  - i. Occluded, or
  - ii.  $\geq 50\%$  in diameter reduction on venography or IVUS, or
  - iii.  $\geq 50\%$  area reduction on IVUS
7. Acute DVT patients should be treated with the Abre stent within 14 days after onset of symptoms. Patients with acute DVT must first undergo successful treatment of acute thrombus ; successful treatment is defined as 30% or less residual thrombus by venogram, as determined by physician, no bleeding, no symptomatic pulmonary embolism (confirmed by imaging), and no renal compromise (renal compromise defined as GFR<30). Patients with underlying obstructive lesions can then be included in the study within the same procedure;
8. Target vessel can accommodate a 9F Sheath, from insertion site to target segment;
9. Exchangeable guidewire must cross target lesion(s) with successful predilation.

---

 Patients subject to the literature review are similar to the subjects that will be included in the study as more than 90% of the patients in the literature review were classified as CEAP 3 or higher.

## 9.5 Exclusion Criteria

Candidates who met any of the following exclusion criteria were not eligible for recruitment in the ABRE study:

### General Exclusion Criteria

1. Patient with DVT in the target limb of which the onset of symptoms is between 15 days and 6 months prior to planned treatment or patient has an acute DVT anywhere else than in the target vessel;
2. Patient has peripheral arterial disease causing symptoms in target limb;
3. Patient is pregnant (female patients of child-bearing potential must have a pregnancy test done within 7 days prior to the index procedure);
4. Patient has a known or suspected systemic infection at the time of the index procedure;
5. Patient has a planned percutaneous or surgical intervention within 30 days prior or 30 days following index procedure, or a contralateral iliofemoral lesion requiring planned treatment within 12 months;
6. Patient requires femoral endovenectomy and patch venoplasty, greater saphenous vein ablation, and/or small saphenous vein stripping during the index procedure;
7. Patient has an active vasculitic inflammatory disorder (e.g. Behcet disease) predisposing the patient to thrombosis and requiring systemic corticosteroid therapy;
8. Patient has impaired renal function (GFR < 30) or is on dialysis;
9. Patient has a platelet count < 50,000 cells/mm^3 or > 1,000,000 cells/mm^3 and/or a WBC < 3,000 cells/mm^3 or > 12,500 cells/mm^3;
10. Patient has a history of bleeding diathesis or either a history or presence of heparin-induced thrombocytopenia antibodies;
11. Patient has a known hypersensitivity or contraindication to antiplatelets or anticoagulation, nitinol, or a contrast sensitivity that cannot be adequately pre-medicated;
12. Patient has presence of other severe co-morbid conditions, which in the investigator's opinion may interfere with the patient's compliance with study visits and procedures, or may confound interpretation of study data (e.g. congestive heart failure Class III and IV, non-ambulatory patients, severe hepatic dysfunction, life expectancy < 1 year);
13. Patient belongs to a vulnerable population per investigator's judgment or patient has any kind of disorder that compromises his/her ability to give written informed consent and/or to comply with study procedures. Patient must be able to consent for themselves;
14. Patient is currently participating in another investigational drug or device study or observational competitive study.

### Imaging-based Exclusion Criteria

15. Patient has a vena cava obstruction or lesion extending into the inferior vena cava (IVC), or the presence of bilateral iliofemoral venous lesions requiring planned treatment within 12 months;
16. Patient has significant venous bleeding, arterial dissection or other injury requiring additional percutaneous or surgical intervention prior to enrollment;
17. Patient has a previously placed stent in the ipsilateral venous vasculature;
18. Patient has disease that precludes safe advancement of the venous stent to the target lesion(s).

## 10 Study Procedures

### 10.1 Schedule of Events

The clinical study required follow-up visits at hospital discharge, 30 days, 6-, 12-, 24-, and 36-months post index procedure. **Table 6** and **Table 7** show a detailed overview of the schedule of clinic evaluations and follow-up visits.

**Table 6: Schedule of Assessments and Visit Windows**

Data Collection Requirement	Screening/Baseline ( $<30$ days before procedure unless otherwise specified)	Procedure	Hospital Discharge	30 Day (-7/+14 days)	6 Months ( $\pm 30$ days)	12 Months ( $\pm 30$ days)	24 & 36 Months ( $\pm 30$ days)	Unscheduled visit for intervention in target vein
Informed Consent	X							
Demographics, Medical History & Physical Examination	X							
Pregnancy Test 	X							
CEAP Classification	X							
Physical Assessment of Limbs	X		X	X	X	X	X	X
Villalta Score, VCSS	X			X	X	X	X	X 
VEINES-QOL/Sym, EQ-5D QOL	X				X	X	X	X 
Procedure Data		X						X
Serum Creatinine, CBC	X							
INR (if on warfarin)	X			X	X	X	X	X
Document Adverse Events	X 	X	X	X	X	X	X	X
Document Device Deficiencies		X	X	X	X	X	X	X
Medication 	X	X	X	X	X	X	X	X
Discontinuation Information 			X	X	X	X	X	X

 Pregnancy test for women of child-bearing potential only. Must be done within 7 days prior to the index procedure.

 Adverse Event assessment need to be done as of the moment the subject is enrolled in the study (i.e. subject signed and dated the informed consent form).

 Medication which will be collected: Antithrombotics, Antibiotics, Immunosuppressants, NSAIDs, Steroids, Diuretics, Calcium-channel blockers, Statins

 Assessments and questionnaires should be taken before any intervention.

 The discontinuation data is needed whenever the subject ends involvement in the study.

**Note:** Only approved devices and therapies may be used during the entire study duration.

**Table 7: Schedule of Imaging Assessments and Visit Window**

Data Collection Requirement	Screening/Baseline (<30 days)	Procedure		Hospital Discharge	30 Day (-7 days, +14 days)	6 Months ( $\pm$ 30 days)	12 Months ( $\pm$ 30 days)	24 & 36 Months ( $\pm$ 30 days)	Unscheduled visit for intervention in target vein
		Pre-stenting	Post-stenting						
Duplex Ultrasound	X			X 	X	X	X 	X	X
Venogram	1	X 	X				4		X
IVUS	1	X 	X						X
X-ray					3		X	X	X 

 Diagnosis can be made during the screening/baseline prior to the index procedure based on objective imaging using venography or IVUS. Diagnosis can also be made during the index procedure, prior to stenting. In case venogram and IVUS are not performed pre-stenting at the time of the index procedure, the pre-procedure venogram and IVUS should be sent to the core laboratory.

If both screening and pre-procedure venogram/IVUS are performed, then the pre-procedure venogram/IVUS should be sent to the core laboratory.

 The DUS examination immediately after the index procedure needs to be performed between 0 and 7 calendar days from the index procedure. When the first examination after the procedure is non-diagnostic, a second examination has to be performed as soon as possible. Every effort should be made to perform this within 7 calendar days after the index procedure.

 X-rays at 30 days will be performed on the first 30 subjects only. They will be assessed for first safety analysis (i.e. stent fracture).

 An additional venogram must be performed when:

- (1) DUS assessment is suggestive of  $\geq 50\%$  restenosis or occlusion per investigator assessment, or;
- (2) when DUS is non-diagnostic or suboptimal such as when a subject is obese (e.g. with a BMI  $> 40$ ), or;
- (3) is clinically required, or in other words when the subject is having symptoms of venous disease in the target limb requiring a venogram.

 Plain x-ray is required pre and post re-intervention to assess for stent fracture.

All imaging examinations as defined in **Table 7** should be performed according to the core laboratory guidelines and will be analyzed by respective independent core laboratories. Exceptionally, the Screening/Baseline Duplex Ultrasound (both limbs) was to be performed according to standard of care and was not required to be sent to the core laboratory.

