#### **Primary safety endpoint**

The primary safety endpoint of this study will be the incidence of composite Major Adverse Events (MAE) at 30 days following stenting of an obstruction in the iliofemoral venous segment. MAEs will be adjudicated by a Clinical Events Committee (CEC), except for stent thrombosis and stent migration as they are confirmed by core laboratory.

The components of the 30-day MAE composite include:

- All-cause death occurring post-procedure
- Clinically significant (i.e. symptomatic, confirmed by CT pulmonary angiography) pulmonary embolism
- Major bleeding complication (procedural)
- Stent thrombosis confirmed by imaging as assessed by core laboratory
- Stent migration confirmed by imaging as assessed by core laboratory

Note: Migration excludes stent dislodgement at the index procedure as may occur with under-sizing of a stent.

---

All subjects will undergo DUS assessments for determination of patency.

An additional venogram must be performed when:

(1) DUS assessment is suggestive of ≥50% restenosis or occlusion per investigator assessment, or  
(2) when DUS is non-diagnostic or suboptimal such as when a patient is obese (e.g. with a BMI >40), or  
(3) is clinically required, or in other words when the patient is having symptoms of venous disease in the target limb requiring a venogram.

All DUS and venographic imaging examinations will be analyzed by respective independent core laboratories.

Clinically driven is defined as the recurrence of symptoms present at baseline or the onset of new symptoms including, but not limited to venous pain, swelling, dermatitis, or ulceration related to the target limb.

Clinically driven target lesion revascularization will be adjudicated by the CEC based on core laboratory adjudicated imaging data and relevant clinical information provided by the site.

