## 10.7 30 Day (-7/+14 days) Post-Procedure Follow-Up Assessment

Subjects were seen in the office at 30 days (23-44 days) post-procedure. The following evaluations were completed and data was recorded on the Follow-up eCRF:

- Physical assessment of limbs;
- Villalta Score and VCSS (both limbs);
- INR for subjects on warfarin;
- Duplex Ultrasound (target limb);
- Duplex ultrasound (contralateral limb); image of the CFV waveform only.

- X-ray (target limb); only on the first 30 subjects in the study for first safety analysis (i.e. stent fracture). Sites will be notified if this is no longer needed;
- Adverse events/device deficiency;
- Medications: Antithrombotics, Antibiotics, Immunosuppressants, NSAIDs, Steroids, Diuretics, Calcium-channel blockers, Statins;
- Discontinuation information (in case the subject ends involvement in the study).

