### **10.12.6.4 X-ray**

During the following timepoints an X-ray (target limb) is required to assess stent fracture:

- at 30-days for first safety analysis for the first 30 subjects;
- at 12, 24, and 36 months for all subjects;
- during reinterventions (unscheduled visits) pre- and post- reintervention.

All X-ray examinations should be performed according to the core laboratory guidelines and are analyzed by an independent core laboratory (See **Section 13.4**).

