**Table 3. Individual Component Event Determination For 30-Day Safety Endpoint**

Primary Safety Endpoint Component Events	Data Source	Event Failure	Individual Endpoint Derivation Rules	Composite Endpoint Derivation Rules
All-cause death	CEC	Event within 30 days post-index procedure by CEC adjudication	Numerator: event-specific, e.g. number of subjects with all-cause death within 30-day post index procedure, will be the numerator for 30-day all-cause death event rate calculation; Denominator: event specific denominator includes any subjects with the event, or subjects had no event but had at least 23-day of clinical follow-up	Numerator: number of subjects with at least one of these five events within 30 days post-index procedure; Denominator: evaluable subjects – any subjects with at least one of these five events, or subjects had none of these five events but had at least 23-day of clinical follow-up
Clinically significant pulmonary embolism	CEC			
Major bleeding complication (procedural)	CEC			
Stent thrombosis	Imaging-Confirmed	Stent thrombosis or migration within 30 days post index-procedure, confirmed by Venogram imaging		
Stent migration	Imaging-Confirmed			

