### 10.3.2 Imaging/Core Laboratory Endpoints

The imaging/core laboratory endpoints include the following:

1. Restenosis (≥50% restenosed of the stented segment of the target lesion) or Occlusion (100% occluded of the stented segment of the target lesion). The imaging assessments are adjudicated by DUS core laboratory or venography core laboratory where applicable;
2. Stent Fracture - assessed by x-ray core laboratory;
3. Delayed Stent Migration (position change of a venous stent observed with an imaging modality >1 cm from its original location at the conclusion of the index procedure, as determined with regard to a reference anatomic structure) - assessed by x-ray or Venography core lab

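### Stent migration counts in the 30-day primary safety endpoint, but no scheduled 30-day image is designated to read stent position, so a silent migration is scored as a non-event

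*Protocol*

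**What the plan says.** - **Endpoint.** Protocol 6.3.1 and SAP 7.9.2 both list migration in the 30-day composite: "Stent migration confirmed by imaging as assessed by core laboratory". The core laboratory, not the Clinical Events Committee, establishes it.
- **Definition.** Protocol Appendix B defines migration for this endpoint as displacement outside the intended treatment segment, seen on an imaging modality that it does not name.
- **30-day imaging.** Protocol 10.7 schedules "Duplex Ultrasound (target limb") for every subject. Table 7 adds "X-rays at 30 days will be performed on the first 30 subjects only", and Protocol 10.12.6.4 repeats the limit: "at 30-days for first safety analysis for the first 30 subjects". Table 7 and Protocol 10.7 give fracture as the purpose of that X-ray. No venogram or IVUS is scheduled at 30 days. Under Protocol 10.12.6.1, a venogram outside the index procedure, a re-intervention and the 12-month criteria is at the investigator's discretion.
- **Who reads it.** Images in Table 7, apart from the screening duplex, "will be analyzed by respective independent core laboratories". Protocol 10.12.6.2 describes follow-up duplex as assessing patency. For the separate endpoint of delayed migration, SAP 10.3.2 names the reading as "assessed by x-ray or Venography core lab"; duplex is not listed.
- **Counting rule.** SAP Table 3 makes venogram confirmation the condition for a 30-day migration. Its denominator takes in "subjects had none of these five events but had at least 23-day of clinical follow-up". Protocol 14.3 and SAP 7.9.2.2 use the same 23-day clinical criterion, with no imaging requirement.

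**The concern.** A component that only imaging can establish needs a planned image read for it. Here the plan designates none at 30 days, and the scoring rule treats the absence of a recorded finding as the absence of the event. The literature review puts migration at 1.4 of the 5.6 percentage points of expected 30-day event rate, a quarter of the planning figure. If some migrations are silent, the observed composite rate is biased down, and the safety test can pass more often than intended when the true rate is at the 12.5% goal. SAP 7.4.2 does not repair this. Its tipping-point analysis concerns missing or unknown outcomes, and these subjects are classed as evaluable and event-free.

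**Working it through.** **1. Reproduce the plan's design figure.** Inputs from SAP 6.3: n = 193, goal 12.5%, expected rate 5.6%, pass if 15 or fewer events.
- P(X ≤ 15 | 193, 0.125) = 0.0249 (SAP: 0.0249).
- P(X ≤ 15 | 193, 0.056) = 0.9233 (SAP: 0.9233).

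The design reproduces.

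**2. Width of the pass line.** Exact one-sided 97.5% upper limits:
- n = 193: 15 events give 12.49% (pass); 16 give 13.11% (fail).
- n = 200: 15 events give 12.07% (pass); 16 give 12.67% (fail).

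At the boundary, one event changes the result.

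**3. Weight of migration.** Appendix A Table IV weighted averages: death 0.0 + thrombosis 2.9 + migration 1.4 + embolism 0.2 + major bleeding 1.1 = 5.6. Share: 1.4/5.6 = 25%. Expected migrations: 0.014 × 193 = 2.7, or 0.014 × 200 = 2.8.

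**4. Scheduled 30-day images against each rule.**

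| Rule | Image that satisfies it | Subjects scheduled for one at 30 days |
|---|---|---|
| SAP Table 3 | Venogram | 0 of 200 |
| SAP 10.3.2 (delayed migration) | X-ray or venogram | 30 of 200, X-ray for fracture |
| Protocol Appendix B | Any modality | 200 of 200 (duplex), but no stated position reading |

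The documents give three different answers, and none of the scheduled images is assigned to stent position.

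**5. Illustration of the effect on the test.** Assumptions: the migration rate is 1.4%; a share s of migrations is missed across all subjects; a missed migration is that subject's only event. The observed rate when the true rate is 12.5% is then q = 0.125 − 0.014 × s, and the chance of passing is P(X ≤ 15 | n, q).

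| s | q | n = 193 | n = 200 |
|---|---|---|---|
| 0 | 0.1250 | 2.5% | 1.6% |
| 0.25 | 0.1215 | 3.4% | 2.3% |
| 0.50 | 0.1180 | 4.7% | 3.2% |
| 1 | 0.1110 | 8.3% | 6.0% |

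The documents do not give s, so the whole range is shown.

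**The case against.** - **Duplex is available for everyone.** It is read by a core laboratory, and Appendix B accepts any modality. The list of modalities in SAP 10.3.2 belongs to a different endpoint. This stands in part: one cannot say that position is unreadable at 30 days. But no section assigns duplex to position, and under SAP Table 3 a duplex finding would not count without a venogram.
- **The tempting stronger reading.** From the X-ray footnote a reader might infer that migration can be read in 30 subjects and not in the other 170. The documents do not support that split. The 30 X-rays are for fracture, and an X-ray would not meet Table 3. By Table 3 all 200 lack a scheduled confirming image; by Appendix B none lacks a scheduled image of some kind.
- **Symptomatic cases will be imaged, and a discretionary venogram is possible at any time.** This stands. The gap concerns silent migrations and those never taken to venogram.
- **The error inflation is assumed.** This stands. With 200 evaluable subjects and a quarter of migrations missed, the chance of passing is 2.3%, still under the nominal 2.5%.
- **The literature rate may share the same under-detection.** Appendix A acknowledges possible under-reporting; 63 of 68 series are retrospective, and 13 of 68 report migration in Table IV. A mismatch between trial and goal is therefore not shown. The scoring of unread subjects as event-free is unaffected.
- **Later X-rays will find persistent displacement.** X-rays at 12, 24 and 36 months are required for all, and delayed migration is cumulative from day 0. This helps, but a finding at 12 months cannot by itself be dated to the first 30 days.

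**Conclusion.** The concern holds in this form: no scheduled 30-day image is designated to read stent position, SAP Table 3 is narrower than Protocol Appendix B on what confirms a migration, and subjects without a position reading enter the denominator as event-free. The direction of any bias is towards a lower event rate. Its size is unknown. The illustration, 2.5% to 8.3% at n = 193 and 1.6% to 6.0% at n = 200, rests on the literature rate of 1.4% and spans every possible missed share; it does not estimate what happened in this trial. The documents do not show that migration was unreadable, that a specific number of subjects was affected, or that the safety test exceeded its nominal level.

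**What to change.** 1. In SAP Table 3, for migration, replace the venogram requirement with confirmation on any core-laboratory-assessed imaging, as in Protocol 6.3.1 and Appendix B. Name the modality read for position at 30 days. The thrombosis row is a separate matter, because Appendix B itself asks for venogram or IVUS there.
2. Report the number of subjects with a core-laboratory position reading by day 44, the close of the 30-day window. Report the 30-day composite with and without migration.
3. Extend the safety tipping-point analysis in SAP 7.4.2 so that migration status is unknown in subjects without such a reading. Include a worst-case bound: apply the migration definition of the primary endpoint to the first later X-ray or venogram already required, and count any migration not shown absent by day 30 as a 30-day event. Label the bound supportive, not a re-test of the 12.5% goal.

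**Cost.** One wording change, two tabulations, one extended sensitivity analysis, and one extra field on reads already made for delayed migration. There is no new imaging. The bound will include some migrations that occurred after day 30 and so is conservative; a bound above 12.5% would not by itself show that the goal was missed. Protocol version 2.0 records that the premarket application has been approved, so these additions would now appear in an SAP amendment and the final report, marked as added after the primary analysis.
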